4.1. Sample size	
4.2. Method of analysis	
5. Ethics	15
6. Finance and indemnity	16
7. Publications	17
8. References	18
Appendix A – Attitudes to Re-irradiation literature search	20
Appendix B – Consent form, Patient Information sheet, Interview structure	21

SYNOPSIS

Study Title:	A qualitative study of patients' attitudes to the risks and potential benefits of radical re-irradiation for lung cancer
Study Design:	Single centre, qualitative interviews
Study Objectives:	
Primary Objective
 
(1) Explore patients' feelings and concerns about having a second course of radiotherapy for recurrent lung cancer
 
Secondary Objectives
 
(1) Identify factors that patients consider when deciding on potential treatments in the setting of locally recurrent lung cancer (including effect of COVID-19 on treatment choice)
 
(2) Investigate how patients' acceptance of side effects changes with the different projected outcomes of re-irradiation
 
(3) Explore the relationship between the toxicities patients experienced during radiotherapy and their attitudes to a second course of radiotherapy
 
(4) Investigate patients' awareness of surveillance imaging after radical treatment and willingness for scans

Study Population:	Patients treated in the West of Scotland Cancer Centre who have completed a course of radical radiotherapy to their thorax for lung cancer
Procedure:	
 • Consent patient during radiotherapy (at radiotherapy on-treatment review clinic) • Confirm consent and arrange interview at 4 weeks after completion of radiotherapy • Semi-structured interview at 5 weeks after completion of radiotherapy (by telephone or video consultation)
Outcome:	Identification of patients' concerns regarding re-irradiation to direct future clinical trial design

1. INTRODUCTION

1.1 *Lung cancer and recurrence*

Lung cancer is the most lethal malignancy in the UK, with over 45,000 people diagnosed each year, and over 39,000 deaths¹. Of those suitable for radical treatment, it is estimated that approximately 45% of lung cancer patients (approximately 5,000 patients in the UK) will have radical radiotherapy to their chest as part of initial treatment². However, there is a substantial risk of either: isolated recurrent thoracic disease (which occurs in 20-30% of patients with non-small cell lung cancer (NSCLC) treated with radiotherapy or chemoradiotherapy^{3,4}) or; development of a second primary lung cancer (the risk of which is 14% over 10 years after initial treatment⁵). There are an estimated 800 patients per year in the UK who may be suitable for further radical treatment yet there are no clear treatment guidelines in this situation.

1.2 *Current treatments for recurrent disease*

For patients with recurrent disease or a metachronous lung primary, treatment options comprise systemic treatment, surgery, or thoracic re-irradiation. Each has risks and potential benefits.

Systemic therapies may be very effective for patients with EGFR mutated, ALK rearranged or PDL1 expressing tumours with disease control lasting for many months or years^{6,7,8}. Unfortunately, this applies to a minority of patients: EGFR mutations and ALK re-arrangements are present in only 10% of NSCLC cases, and high PDL1 levels are seen in 24 to 28%. In patients without these molecular biomarkers, cytotoxic chemotherapy offers a median progression free survival of only 4 months⁹. With all systemic treatments, the patient is continually 'on treatment' and must attend hospital clinics regularly for assessment and blood tests, while experience multiple potential side effects that may be severe enough to cause hospitalisation, the risk of which is up to 68%⁹ for patients receiving cytotoxic chemotherapy. In addition, systemic treatments (with the exception of immunotherapy) rarely offer long-term disease control.

Life extending options for localised disease recurrence are surgery or radical re-irradiation. For surgery, patients need to be fit enough to tolerate a major operation, which is often not the case due to the prevalence of cardiac and respiratory co-morbidities in this group. Radical re-irradiation can offer long-term disease control in selected patients and avoids the risks of surgery. Radiotherapy is generally completed within a few weeks (typically 2-6 weeks), and patients are monitored without treatment until their clinical condition changes, which could be many months or years. This compares well to systemic therapies, where patients would be on 2-4 weekly cycles of treatment until disease progression, with the continual risks of toxicity.

However, re-irradiation may cause severe toxicities in some patients. This is likely to be due to the cumulative dose received by the normal tissues surrounding the tumour. There is limited evidence to predict how normal tissues recover after an initial course of radiation. This means that it is unclear what the cumulative dose limits are for the organs at risk (OAR) in the thorax. Furthermore, some recurrent cancers may be resistant to radiotherapy, leading to concerns

about futility of treatment. Therefore, it is important to develop high quality prospective trials to determine the safety and efficacy of radical re-irradiation.

1.3. Current evidence for radical re-irradiation

Thoracic re-irradiation has been performed since 1963 with variable results and toxicities¹⁰. The benefits are good symptom control when given at palliative doses and long-term disease control in a minority of patients who are radically treated. There is currently a lack of high level evidence to inform clinicians of the safety and efficacy of radical re-irradiation, with only one prospective phase 1 study evaluating thoracic re-irradiation and several retrospective reviews¹¹.

The phase I study (Wu *et al.* 2003) evaluated radical dose, conventionally fractionated re-irradiation to recurrent lung cancers in 23 patients, who received a median dose of 66 Gray (Gy) at first treatment, and 51 Gy at re-irradiation. Median overall survival (OS) from re-irradiation was 14 months (range 2-37), with no acute grade 3 or greater toxicities recorded (RTOG grading). There was a 22% rate of grade 1-2 pneumonitis and 9% rate of grade 1-2 oesophagitis. There have been several retrospective reviews of re-irradiation using radical doses and conventional fractionation^{12,13,14,15,16}. For radical dose re-irradiation, median OS in these reviews ranged from 7.1 to 13.5 months with 1 year local control rates of 57% to 66%. The radiotherapy techniques used in these studies are often outdated (e.g. 3D conformal radiotherapy) and have methodological flaws including inaccurate toxicity reporting since they are database reviews, rather than prospective trials.

1.4. Need for a prospective trial of radical re-irradiation

Local data from the Beatson West of Scotland Cancer Centre demonstrates that only 6.7% of the expected number of patients who may be eligible for re-irradiation receive this treatment. Reasons for the low uptake of this treatment include: limited prospective trial data demonstrating efficacy, concerns about safety, no clear guidance on surveillance post-radical radiotherapy leading variable detection of recurrence and patient refusal. A Canadian working group documented clinician's opinions on offering re-irradiation, with 35% declining to re-treat a standardized case¹⁷. As there clearly are different opinions on optimal treatment for patients with recurrent disease, a contemporary prospective clinical trial is warranted. The outcomes of this study would be robust data on safety, local control and overall survival. This will help develop treatment options for patients with recurrent disease. A recent survey of UK clinical oncologists demonstrates widespread enthusiasm for contemporary re-irradiation studies, with 76% of responders interested in further research on this topic¹⁸.

1.5. Patient attitudes to re-irradiation

The key aim of this study is to elucidate patients' concerns about re-irradiation. This information is needed to firstly assess whether patients would accept re-irradiation as a treatment. Secondly, any barriers to participation identified in this qualitative study can be addressed in the clinical trial design. A literature search yielded no published data regarding patient acceptance or patient experience of re-irradiation for any tumour groups (see Appendix A). There could be many reasons why patients do not want to have re-irradiation

such as reluctance to undergo uncomfortable repeat investigations, issues regarding transport to the radiotherapy centre, side effects from the original treatment or anxiety about experimental treatment. Awareness of patients' concerns about re-irradiation is crucial to develop a feasible clinical trial.

1.6. Patients' consideration of alternative treatments in the locally recurrent setting

As previously mentioned, no guidelines exist for the treatment of locally recurrent lung cancer. The choices for patients include systemic treatment, radical radiotherapy or a watch and wait strategy in asymptomatic patients. How patients choose between these treatment options is important to explore because any randomization in a prospective trial will need both equipoise from the clinician, but also patient agreement that either treatment arm is appropriate. There are no published data on this topic. This discussion is particularly pertinent during the COVID-19 pandemic as patients and clinicians attempt to reduce the amount of hospital visits and treatments that could deplete the immune system. This interview study will identify what treatments patients would agree to, thereby improving the future trial design.

1.7. Relationship of symptoms from initial radiotherapy and willingness for re-treatment

Joseph *et al.*, when reporting a re-irradiation workshop, stated that patients who tolerated initial radiotherapy poorly were unsuitable for re-irradiation¹⁷. This refers to clinicians' concerns of causing severe toxicity with re-irradiation and may be a barrier to successful trial recruitment. Historically, re-irradiation has a significant risk of toxicity. The rates of severe toxicity may be lower using the newly published cumulative dose constraints, although these need validation. There are no prospective published data regarding whether patients who have toxicities are less likely to want further treatment. There is a need to identify if there is a relationship between the severity of patients' symptoms during initial treatment and their willingness for re-irradiation. This study will explore whether, despite toxicities from first the first radiotherapy course, patients still would consider aggressive re-treatment, and if so, what changes would they want to make their second course of radiotherapy more tolerable.

1.8. Patients' attitude to risk of toxicity

The safety of the prospective re-irradiation clinical trial depends in part on the use of cumulative dose constraints to the normal tissue OARs. The evidence for re-irradiation dose constraints is limited. In general, the higher the cumulative dose to an OAR, the greater the risk of toxicity. There is no published evidence describing patient's attitude to risk, and what toxicities they would accept for a given outcome.

In addition, new radiotherapy technology has become available to distribute the dose of radiotherapy across different OARs. The first iteration of this approach is intensity modulated radiotherapy (IMRT) which is now the standard of care for radiotherapy in many tumour sites. The benefit of this approach is to reduce the areas receiving a high dose of radiotherapy, but increase the area receiving a low dose bath. By reducing the OARs receiving the highest dose, the side effects patients develop are reduced.

One development of IMRT is multi-criteria optimisation (MCO). This uses a planning algorithm which generates multiple plans simultaneously. This allows the clinician to keep the tumour dose the same, but shift the dose from different OARs, to achieve the best plan. Recent work has demonstrated that using MCO in re-irradiation planning can reduce dose to the oesophagus significantly, at the cost of increasing the dose to the lungs¹⁹. The significance for the patient is that the clinician is reducing the risk of oesophagitis and swallowing difficulties, but increasing the risk of pneumonitis and breathlessness. There is no published evidence describing what side effects lung cancer patients would accept and, if they had to have a side-effect, which would they prefer. Further research into this will guide clinicians to make treatment planning decisions with patient input.

1.9. Attitudes to surveillance after radical radiotherapy

Any future prospective trial in recurrent lung cancer requires timely detection of local relapse. Recent guidelines have suggested surveillance CT scans every 6 months to detect recurrent disease, although the strength of evidence supporting these recommendations are weak. The majority of studies focus on the overall benefits that surveillance has on outcome and very few report on patient's quality of life. This interview study will explore patients' attitudes to surveillance scanning, and discuss the benefits and risks of either approach. Further information on this is important in the context of a re-irradiation trial as it is anticipated that surveillance CT scans will be a key method of identifying suitable trial patients.

1.10. Rationale and Summary

A prospective clinical trial to evaluate radical re-irradiation for lung cancer is urgently needed, as there are no contemporary robust trial data about this treatment. The results could have significant benefits for an under-served lung cancer population, by finding out which patients should receive re-irradiation, and how to deliver re-irradiation safely. However, to ensure that this interventional trial is designed appropriately and that it recruits well, it is necessary to interview patients who have already completed one course of radiotherapy. This group of patients have been chosen because they would be eligible for the re-irradiation clinical trial, and they have experienced radical lung radiotherapy and its side-effects.

The purpose of this qualitative study is to discover what the potential barriers to accepting re-irradiation are, explore patients' attitudes to alternative treatments for local recurrence, what side effects are most concerning, and acceptance of surveillance CT scans. To be able to explore fully patients' concerns and attitudes, semi-structured interviews will be conducted. The interviews will take place after patients have completed their first course of radiotherapy. The information learnt from these patients' experience will shape a future re-irradiation prospective trial protocol to ensure that it is both acceptable to patients and clinically relevant.

2. AIMS AND OBJECTIVES

2.1 *Aims*

The aim of this study is to explore patients' experience of radical radiotherapy for lung cancer and their attitudes to having a second treatment.

2.2. *Primary Objectives*

- (1) Explore patients' feelings and concerns about having a second course of radiotherapy

2.3. *Secondary Objectives*

- (1) Identify factors that patients consider when deciding on potential treatments in the setting of locally recurrent lung cancer (including effect of COVID-19 on treatment choice)
- (2) Investigate how patients' acceptance of side effects changes with the different projected outcomes of re-irradiation
- (3) Explore the relationship between the toxicities patients experienced during radiotherapy and their attitudes to a second course of radiotherapy
- (4) Investigate patients' awareness of surveillance imaging after radical treatment and willingness for scans

3. METHODOLOGY

3.1. *Study design*

This is a qualitative interview study. The semi-structured qualitative interviews will take place after radiotherapy is completed and explore positive and negative aspects of that treatment, followed by discussion about concerns about re-irradiation, and risk of side-effects. Figure 1 provides an overview of the study design.

3.2. *Inclusion and Exclusion Criteria*

Patients must meet all of the following inclusion criteria to be considered for this study:

- Age 18 years old or above
- Pathological or radiological diagnosis of non-small cell lung cancer
- Undergoing radical radiotherapy to the thorax using the following fractionations (55 Gray in 20 fractions, 54 Gray in 36 fractions or any Stereotactic Ablative Body Radiotherapy (SABR) fractionation that delivers a biological effective dose of greater than 100Gy₁₀) as part of their primary lung cancer treatment at time of study enrolment
- Patients receiving concurrent and/or adjuvant systemic therapies are permitted
- Radiotherapy is delivered in the Beatson West of Scotland Cancer Centre
- Signed, written informed consent
- Willing and able to complete study processes

Patients who meet any of the following exclusion criteria will not be enrolled on to the study:

- Not fluent in English

3.3. *Recruitment and sampling*

In order to ensure adequate representation of patients receiving systemic treatment and different types of radiotherapy (as their experience of treatment will vary considerably), four patients will be recruited from each of the following radiotherapy sub-types: SABR, Continuous hyperfractionated accelerated radiotherapy CHART, concurrent chemoradiotherapy and radiotherapy alone.

For patients undergoing SABR, they will be approached by a radiographer at their mould room appointment, where the aims of the study and the study procedures will be explained, and participant information sheet will be given to them. They will then have approximately 3 weeks to consider this information. When they return to have their radiotherapy, the radiographer will enquire if they wish to be involved in this study. If so, they will be seen by the researcher for consent on the same day.

Patients receiving CHART, concurrent chemoradiotherapy, or radiotherapy alone, will be recruited through the on-treatment review clinic. This clinic at the Beatson West of Scotland Cancer Centre is where patients having radical radiotherapy are monitored every week during their treatment. It is staffed by clinical nurse specialists and radiographers. They will pre-screen new patients attending their first/second on-treatment review clinic during the first

two weeks of radical radiotherapy. Patients who meet the inclusion criteria will be approached by the clinical nurse specialist/radiographer in the clinic. The aim of the study and the study rationale will be described and an information sheet will be given to the patients (see Appendix B).

3.4. Consent

When the patient returns to the Beatson for the on-treatment radiotherapy review in the following week (i.e. the second/third week of treatment), or in the first week of radiotherapy treatment for patients receiving SABR, the nurse specialist/radiographer will ask the patient if they would like to discuss the study with the researcher. If the patient agrees, the patient will meet the researcher and answer any questions. If the patient wishes to participate in the study, they will complete three consent forms with the researcher, one for the patient to keep, one for the site file and one for the medical notes. Consent will be re-confirmed at the pre-interview phone call and at the start of the interview. If the patient would like to conduct the interview using the NHS Anywhere virtual consultation platform, a web address will be given to the patient at this point.

3.5. *Semi-structured interview*

The patient and the researcher will arrange a mutually convenient time for the qualitative interview 4 weeks after completion of radiotherapy (+/- 5 days). On this pre-interview call, the patient will also re-confirm the consent to be involved in this study. If the patient wished to use the NHS Anywhere platform, then the web address will be also re-confirmed with them. Patients will also be invited to have a family member or friend nearby for the interview to offer support if needed. The interview will be performed after 5 weeks as it allows for most of the acute side effects of treatment to subside, but the patient would not have any idea of how effective the treatment has been, as this may bias their answers. The interview will be done either over the telephone or using the NHS Anywhere virtual consultation platform. The interview will be recorded. At the start of the interview, consent will also be re-confirmed. The structure of the interview is documented in Appendix B.

As some of the topics of the interview could be distressing, if at any point during the interview the patient becomes upset, the interview will be paused and the patient given time to recover. The interview can proceed again only once the patient agrees to do so, otherwise the interview will be permanently stopped. As the interview will be conducted over the telephone, if the patient needs further support and consents to it, the researcher will contact the patient's clinical team and request that they contact the patient to offer further care. In addition, the patient may have a member of family or a friend with them to assist them. The patient will also have a routine follow-up visit with their clinical team one week after the interview, where they may wish to discuss any issues which have arisen from the interview.

During the interview, if the patient describes any symptoms or issues that require medical attention the researcher may inform the patients' clinical team with the patients' consent. The recording of the interview will be anonymised, transcribed and stored securely on the NHS IT systems.

[figure not shown]

Figure 1. Study schema

3.6. *End of study*

The patient will have completed the study once the interview has ended. They will be given the option to be kept informed about the outcomes of the study and ongoing work. At any point, patients can withdraw from the study with no change to their medical treatment. Once the patient has left the study, they will be followed-up as per standard practice of their treating clinical oncologist.

3.7. *Potential risks and benefits*

The principal risk of this study is that any discussion of traumatic experiences such as being unwell or relapse after arduous treatment can cause significant psychological harm. The steps taken to mitigate this risk are to inform the patient from the outset of the topics that will be discussed in the interview in both the patient information sheet and in the consent process. If the patient becomes distressed in the interview, then the interview will be halted and further support offered (from the patient's regular clinical team, and, if the patient has agreed, a member of their family or a friend).

The patient will have no direct benefit from taking part in this study as this study does not involve any change in the medical care that the patient receives. However, the results from the study will help the design of a prospective trial of re-irradiation, and this will improve the safety of this treatment for future patients. Additionally, the results of these interviews may identify areas to improve the patient experience in patients having initial radiotherapy at the Beatson West of Scotland Cancer Centre.

3.8. *Mitigation for SARS-CoV-2*

The WHO declared a global pandemic in response to the novel severe acute respiratory syndrome coronavirus-2 (SARS-CoV-2) in early 2020. In order to limit patients' exposure to potential infectious contacts, this study will perform most of the study procedures over either the telephone or using secure remote consultation software. The patient will meet the researcher in person only once, when consent is being taken, at the same time as they are attending the on-treatment radiotherapy review clinic, thus reducing the need for additional visits to hospital.

3.9. *Data storage and retention*

The interviews will be recorded on to the Winscribe system (this is the system used for recording clinic dictations in the Beatson). The recordings will be password protected. They will be transcribed either by the researcher, or NHS clerical staff. The original recordings will be stored securely on the NHS IT system until the end of the study, as source data in case of audit. Once the trial is complete, the source recordings will be destroyed. The source recording will be transcribed and anonymised. The anonymised transcripts will be transferred to the University of Glasgow IT systems for analysis using NVivo software. Once analysis is complete, this study will be written for publication. The anonymised transcribed source data will be uploaded on to the Enlighten data repository curated by the University of Glasgow, where it will be kept for at least 10 years and will be accessible to other

researchers on application as per the University of Glasgow data protection policy.
Anonymised data from this study may be used in other studies if appropriate.

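### Do the two wordings of the interview date, and the silence on patients who stop radiotherapy early, require a change to the protocol?

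*Protocol*

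**What the plan says.** **Timing.** The synopsis procedure lists consent during radiotherapy, then a step at 4 weeks to confirm consent and fix the appointment, then "Semi-structured interview at 5 weeks after completion of radiotherapy". Section 3.5 says patient and researcher will "arrange a mutually convenient time for the qualitative interview 4 weeks after completion of radiotherapy (+/- 5 days", and its next sentence calls this contact the pre-interview call. It then says "The interview will be performed after 5 weeks as it allows for most of the acute side effects of treatment to subside", adding that by then the patient would not yet know how well treatment had worked, since that knowledge could bias the answers. On support after a distressing interview, 3.5 adds: "The patient will also have a routine follow-up visit with their clinical team one week after the interview". Section 3.7 says "this study does not involve any change in the medical care that the patient receives".

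**Who is interviewed.** Section 3.2 enrols patients who are undergoing radical radiotherapy "as part of their primary lung cancer treatment at time of study enrolment". The synopsis defines the population as patients who have completed a course. Section 1.10 says "it is necessary to interview patients who have already completed one course of radiotherapy", and 3.1 places the interviews after treatment is finished. Section 3.6 lets a patient withdraw at any point; it does not mention a course of radiotherapy that ends early.

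**Numbers.** Section 3.3 says "four patients will be recruited from each of the following radiotherapy sub-types", and there are four sub-types. Section 4.1 sets a minimum of 16 and allows recruitment up to 30 if saturation is not reached.

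**The concern.** Two things look wrong on a first reading.

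First, the synopsis gives a point in time and 3.5 gives a lower limit with no upper one. The one tolerance is attached to week 4, in a sentence that, taken alone, could be read as placing the interview itself there. Section 3.5 relies on the timing in both directions: late enough for acute effects to settle, early enough that the outcome is unknown. It also counts on a clinic visit a week later. If that visit is routine and the study alters no care, a late interview would shorten the gap, or could even follow the visit.

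Second, patients enter before anyone knows whether they will finish radiotherapy, but every later date runs from completion. If some stop because of toxicity and drop out uncounted, secondary objective 3 (toxicity experienced against attitude to a second course), and the planned severity-by-willingness comparison in 4.2, could lose patients at the severe end without a reader seeing it.

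**Working it through.** **1. Do the timing statements conflict?** Counting days from completion of radiotherapy:

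- Week-4 step with its tolerance: 28 − 5 = 23 to 28 + 5 = 33.
- Interview at 5 weeks: 5 × 7 = 35.
- Gap from call to interview: 35 − 33 = 2 days at least, 35 − 23 = 12 days at most.

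If the tolerance belonged to the interview, its window (days 23 to 33) would never reach day 35, so the paragraph would contradict its own 5-week statement. If it belongs to the call, everything fits: call on days 23 to 33, interview from day 35. The synopsis separates the two steps in this way, and the sentence in 3.5 after the tolerance names the contact as the call. Only the second reading is tenable. The wordings at and after 5 weeks are both met on day 35.

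**2. How much slack is there before the visit?** The text dates the visit only relative to the interview. Assuming it is fixed by an interview on the nominal day, it falls on 35 + 7 = day 42. An interview that slips by *s* days leaves 7 − *s* days before the visit, so the order holds for any slip under 7 days. Even after the latest permitted call there are 42 − 33 = 9 days before the visit. The visible text mentions no assessment of response between week 5 and that visit.

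**3. Sample size.** The plan's figure reproduces: 4 sub-types × 4 patients = 16, the stated minimum. It rests on saturation, so there is no power calculation to disturb.

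**4. What would early stopping cost?** One consented patient not interviewed leaves 3/4 = 75% of that sub-type and 15/16 = 93.75% overall. The protocol gives no early-stop rate, so the rates *d* below are assumptions. The chance of at least one among *n* is 1 − (1 − *d*)^*n*. The consents needed for 16 expected completers are 16/(1 − *d*), rounded up.

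| Assumed *d* | At least one of 16 | At least one of 4 | Consents needed |
|---|---|---|---|
| 2% | 28% | 8% | 17 |
| 5% | 56% | 19% | 17 |
| 10% | 82% | 34% | 18 |
| 15% | 93% | 48% | 19 |

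For example, at 10%: 1 − 0.9^16 = 0.815, and 16/0.9 = 17.8, rounded up to 18. At least one early stop is quite possible, but replacing such patients needs at most 3 extra consents over this range, against 30 − 16 = 14 places above the minimum.

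**The case for a change.** The best argument for a change is that the protocol itself names a bias that depends on an upper time limit, and then writes no upper limit. It also names psychological harm as the principal risk in 3.7 and offers the later visit as one support, without tying the visit date to the interview date. On numbers, the quota counts patients recruited, so read literally a consented patient who is never interviewed still fills a place, and recruitment beyond 16 is triggered by lack of saturation, not by a lost interview. Scheduling and the handling of consented patients are procedures that a protocol normally settles itself.

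Part of this stands. The visible text does lack a tolerance for week 5 and a rule for counting non-completers. The rest is weaker. The schema in Figure 1 is a natural place for a visit window and is not available, so its absence from the plan cannot be asserted. The fixed day-42 visit is inferred; the text simply puts the visit a week after the interview. The visit is also one support among several: 3.5 provides for pausing or stopping the interview, contact with the clinical team, and a relative or friend being present. As for lost interviews, saturation is judged on interviews actually held, so a shortfall that left themes incomplete would itself prompt further recruitment. That protects the overall number, though it does not guarantee four interviews in each sub-type.

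**Conclusion.** No change to the plan follows. The timing passages are awkwardly drafted but do not contradict each other, and a researcher reading 3.5 with the synopsis would ring at about week 4, interview at about week 5, and precede the routine visit. An unwritten tolerance of a few days on a mutually convenient appointment is a gap that sensible conduct fills.

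The silence on early stoppers leaves the target group clear. The synopsis, 1.10 and 3.1 show that the study is about patients who have finished a course, and followed as written it gives sound findings for them. Those findings should be read as applying to completers, and a normal account of participant flow would show how many consented patients were not interviewed.

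In size, the effect is at most one or a few interviews in a qualitative study with a minimum of 16 and a ceiling of 30. No stated number or test changes. Any distortion of the link between toxicity and willingness is conjecture: the protocol gives neither an early-stop rate nor the reasons for stopping, so its size and direction cannot be derived. This conclusion assumes that Figure 1 and Appendix B, which were not available, contain nothing that conflicts with the text of 3.5.
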